2.3.2 Accelerated RRT initiation (experimental arm)

A dialysis catheter will be placed and RRT initiated as soon as possible and within 12 hours of eligibility. This 12-hour window includes the time needed to obtain consent or, where permissible, to document enrollment by deferred/delayed consent.

2.3.3 Standard RRT initiation (control arm)

This treatment arm comprises a strategy of conservative management with respect to RRT initiation and RRT will only be initiated in the presence of the criteria below:

- a) Persistent severe AKI defined as sCr that remains > 50% of the value recorded at randomization

AND at least one of the following indications for RRT initiation:

- a) Serum potassium ≥ 6.0 mmol/L, or
- b) pH ≤ 7.20 or serum bicarbonate ≤ 12 mmol/L, or
- c) Evidence of severe respiratory failure, based on a PaO₂/FiO₂ ≤ 200 and clinical perception of volume overload, or
- d) Persistent severe AKI (sCr remains > 50% the value recorded at randomization) for > 72 hours from randomization

Patients will be evaluated on a daily basis by research staff to ascertain the presence of indications for RRT and provide consistent reminders to clinicians about study-prescribed criteria for RRT initiation. Clinicians will be asked to not initiate RRT unless the above criteria are present. By the same token, the clinician is not obligated to commence RRT even if the above conditions are met. However, the experience from the pilot phase of this program showed that two-thirds of patients in the standard arm commenced RRT in the absence of meeting the above criteria highlighting the challenges of absolutely restricting the application of this therapy in the realities of clinical practice. Thus, RRT may still be commenced in the standard RRT initiation arm anytime at the discretion of the attending clinician(s) based on clinical judgment. The clinician will be asked to specify the primary reason for initiating RRT in the absence of meeting the trial-specified criteria. However, initiation of RRT within 12 hours of eligibility will be considered a protocol violation and the clinician will also be asked to provide the primary reason(s) for RRT commencement. The decision to initiate RRT in the standard

arm of the trial will have to be approved by the **attending physician(s)** involved in the patient's care.

Once a decision is made to start RRT, a dialysis catheter will be placed and RRT initiated as soon as possible. In the standard initiation group, it is expected that a proportion of participants may die before receiving RRT while others may experience recovery of kidney function thus obviating the need for RRT.

2.3.4 RRT delivery in the STARRT-AKI Trial

Other than the study intervention (i.e., differential timing of RRT initiation), all RRT delivered to patients in both treatment arms will follow an identical set of recommended guidelines that is compatible with contemporary clinical practice as described in the study Operations Manual.

2.3.5 Criteria for discontinuation of renal replacement therapy

Once started in either treatment arm, RRT will continue until one of the following circumstances is encountered:

- 1- Death; or
- 2- Withdrawal of life support in the context of a change in the goals of care; or
- 3- Kidney function recovery with no need for continued RRT as per the nephrologist's or critical care physician's judgment. Guidance regarding the presence of renal recovery is found in the Operations Manual. RRT may be reinitiated at any time according to the same principles described in the Operations Manual.

2.4 Frequency and duration of follow-up

Each participant will be followed for up to 90 days following randomization, and where feasible, to one year from randomization using administrative data.

Patients randomized to accelerated RRT initiation: After consent has been obtained from the patient or SDM (or enrollment by deferred/delayed consent documented), patients will be assessed frequently in order to ensure that the randomized intervention is correctly implemented (i.e., within 12 hours of eligibility). Study personnel will provide regular reminders to the clinical team until RRT is started. Even after 12 hours have elapsed, the study team will encourage the initiation of RRT as soon as possible. Reasons for delays will be recorded.

Patients randomized to the standard RRT initiation strategy: Clinical and laboratory data will be reviewed daily for 14 days after randomization and clinicians will be notified if any indications have developed that prompt consideration of RRT initiation based on the criteria listed in Section 2.3.3. The initiation of RRT in a patient allocated to the standard arm must be approved by the attending physicians.

Patients in both arms will receive identical daily follow-up from randomization until Day 14 for assessment of clinical and physiologic data. We will also monitor and collect data on all RRT that is administered during the first 14 days after randomization. Similarly, we will collect data on safety events during this time period. Each participant will be followed to 90 days following

randomization and, where feasible, overall follow-up (using administrative databases and a phone call to ascertain quality of life) will conclude at 365 days following randomization.

2.5 Outcomes

2.5.1 Primary outcome

The primary outcome will be all-cause mortality within 90 days of randomization. We chose this as our primary outcome as it is least susceptible to bias in an unblinded trial, is reliably captured and is of unquestionable clinical relevance. All-cause mortality has also been used as the primary outcome in all major trials involving RRT interventions in the ICU.^{20,21,23}

2.5.2 Secondary outcomes

- 1 - RRT dependence at 90 days among surviving patients.
- 2 - Composite of death or RRT dependence at 90 days.
- 3 - Estimated glomerular filtration rate among patients alive at Day 90.
- 4 - Albuminuria at Day 90.
- 5 - Major adverse kidney outcomes, defined as death, RRT dependence or sustained reduction in kidney function (defined as eGFR < 75% baseline eGFR) at 90 days.
- 6 - Mechanical ventilation-free days through day 28.
- 7 - Vasoactive therapy-free days through day 28.
- 8- ICU-free days through day 28.
- 9 - Hospitalization-free days through day 90.
- 10 - Death in ICU, at 28 days, and in-hospital.
- 11 - EuroQoL EQ-5D-5L (a measure of health-related quality of life and patient utility) at day 90 and at 1 year among survivors.
- 12 - Health care costs through day 365.
- 13 – Vital status and RRT dependence at 365 days among survivors.

2.5.3 Safety events

The following events related, all felt to be clinically significant consequences of the receipt of RRT, will be recorded through Day 14 (specific details on ascertainment of each event are found in the Operations Manual):

1 - RRT-associated hypotension

Defined as: A drop in blood pressure requiring one of: initiation of a vasopressor during RRT session or need to escalate dose of a vasopressor during the RRT session or premature discontinuation of RRT session due to hypotension.

2 - Severe hypophosphatemia

Defined as: Serum phosphorus < 0.5 mmol/L on any bloodwork.

3 - Severe hypokalemia

Defined as: Serum potassium < 3.0 mmol/L on any bloodwork.

4 - Severe hypocalcemia

Defined as: Albumin-adjusted serum calcium < 1.90 mmol/L or ionized calcium < 0.90 mmol/L.

5 - Allergic reaction

Defined as: Clinician suspicion of allergic reaction to one of the components of the RRT apparatus.

6 - Arrhythmia during RRT

Defined as: New atrial (excluding sinus tachycardia or sinus arrhythmia) or ventricular arrhythmia that develops during RRT and was not present prior to initiation of RRT that requires treatment with any medication or cardioversion/defibrillation or decision to stop RRT prematurely as a result of arrhythmia.

7 - Seizure

Defined as: Seizure that develops during RRT session and confirmed by attending clinician.

8 - Major Bleeding

Defined as:

- a) Life threatening bleeding and associated hypovolemic shock (e.g., from ruptured abdominal aortic aneurysm or upper or lower gastrointestinal hemorrhage).
- b) Life threatening bleeding at a critical site (e.g., intracranial, retroperitoneal, pericardial).
- c) Overt, clinically important bleeding associated with one of the following within 24 hours of the bleed: decrease in hemoglobin >20 g/L or transfusion \geq 2 packed red blood cells.
- d) Bleeding requiring an invasive intervention (e.g., re-operation).

2.5.4 Safety events potentially related to the central venous catheter (CVC) used for RRT

The following events related, all felt to be clinically significant consequences of the receipt of the CVC used for RRT, will be recorded through Day 14 (specific details on ascertainment of each event are found in the Operations Manual):

1 - Hemorrhage at the site of CVC insertion

Defined as: Bleeding described by clinician inserting catheter requiring transfusion of \geq 1 unit(s) of packed red blood cells and/or surgical intervention/repair within 12 hours following insertion.

2 - CVC-associated bloodstream infection

Defined as: Bloodstream infection in 2 blood culture sets (one drawn from dialysis catheter and the other from another site) with no proven alternative source for bloodstream infection as per ICU attending OR culture-positive recovery of the same organism from the dialysis catheter upon removal.

3 - Ultrasonographically-confirmed thrombus attributed to CVC

Defined as: Any confirmed occlusive or non-occlusive thrombus in the vein in which a CVC for RRT was placed (or remains in place) or in the venous system drained by the vein in

which the CVC was placed; further qualified by pulmonary embolism as a result of thrombus.

4 - Pneumothorax (for catheters placed in the internal jugular or subclavian positions)

Defined as: Air in the pleural space on routine chest x-ray that is performed following CVC insertion; further qualified by requirement for chest tube placement.

5 - Hemothorax (for catheters placed in the internal jugular or subclavian positions)

Defined as: Blood in the pleural space following CVC insertion; further qualified by requirement for chest tube placement.

6 - Air embolism

7 - Inadvertent arterial puncture at time of CVC insertion

8 - Other CVC-related safety events

2.6 Safety outcomes

All deaths that occur during the 14-day follow-up period will be reviewed by the local investigators in coordination with attending clinicians in order to determine whether these may be linked to participation in the trial. We will also collect data on safety events with a focus on those related to the administration of RRT and the associated need for vascular access as described above. The local research team will determine whether these events qualify as serious adverse events (see definition below).

2.6.1 Definition of a serious adverse event

The standard definition of a serious adverse event (SAE) includes any adverse event that meets at least one of the following conditions:

- is fatal (results in death)
- is felt to be life-threatening
- requires in-patient hospitalization or prolongation of an existing hospitalization
- results in significant disability or incapacity

For this study, a reportable SAE must meet the definition noted above and also be considered⁴⁵:

- i. an atypical event, defined as clinically significant and unexpected in the context of critical illness secondary to AKI, AND;
- ii. an event that is at least possibly related to study procedures.

For reportable SAEs that occur from the time of patient consent/enrollment until Day 14, the following reporting procedure applies:

- Report using the Adverse Event Form of the eCRF within 1 business day of becoming aware of the event.
- Document in source records.
- Follow-up of any SAE that is fatal or life threatening should be provided within 7 calendar days.

- Follow-up the outcome of SAEs until clinical recovery is complete and laboratory results have returned to baseline, or until progression has been stabilized. Follow-up will continue for the duration of the patient's study participation.

Local reporting requirements may differ from those of the trial. The local investigator will be responsible for reporting SAEs to their Ethics Board as per institutional requirements.

2.7 Measurement of outcomes

2.7.1 Primary outcome

We will access hospital records (both study hospital and facilities to which patients may be transferred), consult primary care physicians, contact participants/SDMs, and if needed, access death registries to ascertain vital status at 90 days.

2.7.2 Secondary outcomes

- 1 - RRT dependence will be defined by the receipt of any form of RRT within +/- 14 days of the 90-day time point following randomization.
- 2 - The composite outcome of death by Day 90 (primary outcome) or RRT dependence at Day 90 (principal secondary outcome).
- 3 - We will evaluate kidney function in all patients alive at Day 90. Serum creatinine will be drawn at Day 90 (or as close as possible to Day 90) and not beyond 132 days after randomization (i.e., we will accept a serum creatinine value from Day 90 minus 14 days or Day 90 plus 42 days). eGFR will be derived from the CKD-EPI equation and expressed in mL/min/1.73 m².⁴²
- 4 - A urine sample will be obtained at Day 90 (or as close as possible to Day 90) and not beyond 132 days after randomization (i.e., Day 90 minus 14 days or Day 90 plus 42 days) for assessment of spot albumin and creatinine concentrations.
- 5 - Major adverse kidney event (MAKE) by Day 90 (defined as the composite of death, RRT dependence or sustained reduction in kidney function [defined as Day 90 eGFR < 75% baseline eGFR]).
- 6 - A ventilator-free day will be defined as the receipt of < 2 hours of either invasive or non-invasive ventilation within a 24-hour period.
- 7 - A vasoactive-free day will be defined as < 2 hours of receipt of any vasoactive therapy provided by continuous infusion within a 24 hour period.
- 8 - An ICU-free day will be defined as admission to an ICU for < 2 hours within a 24 hours period.
- 9 - Hospital-free days will be defined as a 24-hour period completely free of an inpatient hospitalization.
- 10 - Death in ICU, at 28-days and in-hospital will be compared between the groups.
- 11 - The EuroQol EQ-5D-5L questionnaire will be used to measure health-related quality of life. As a widely accepted measure of patient utility, the EQ-5D-5L can be converted to quality-adjusted life years (QALYs) for use in the economic evaluation.
- 12 - The economic evaluation will include the cost of the strategy itself (which will be assessed using a micro-costing approach⁴⁶), plus any implications on length of stay, safety events associated with an accelerated or standard initiation strategy, and the costs associated with RRT use after ICU discharge up to 365 days from randomization. To measure these

impacts, we will assess hospital and ICU use, physician claims, and subsequent outpatient claims for RRT for all patients within the trial. Consistent with usual practice within a multicentre clinical trial, valuation of costs will be done for the subset of all patients enrolled within the province of Alberta, Canada (extrapolated based on resource use for all patients in the trial) using administrative costing data available from Alberta Health Services, and from the Alberta Physicians' fee schedule, using methods familiar to study investigators⁴⁶.

- 13 - In jurisdictions where this is feasible, we will access administrative data to ascertain vital status and the need for RRT at Day 365 from randomization. RRT dependence will be defined by the patient having a kidney transplant or the receipt of any form of RRT within +/- 14 days of the 365-day time point following randomization.

2.8 Health resource utilization analysis

Given that a strategy of accelerated RRT initiation is likely to increase short-term resource use, assessing the implications on long-term health outcomes and costs is important. Since we will be assessing survival, RRT dependence, patient utility, and costs, we will be able to conduct a full economic evaluation of accelerated RRT initiation in patients who have AKI.

Consistent with current guidelines, we will use the perspective of the publicly funded health care system. As noted above, we will carefully measure the cost of the intervention, as well as any associated and downstream costs. We will also estimate "time and travel" costs for patients in the trial, based on the subsequent need for RRT therapy.⁴⁸

If RRT dependence at 90 days differs between the two treatment arms, then extrapolation of the benefits and costs beyond the timeframe of the clinical trial will be required to assess the complete economic implications of this strategy. This will be critical to justifying (or not) the use of this strategy to health care payers. To enable this, a decision analytical framework will be developed alongside the data from the clinical trial to model the potential impact of accelerated RRT initiation on long-term outcomes and costs, using a lifetime perspective. Sensitivity analysis will be undertaken to account for uncertainty regarding the long-term estimated costs and effects.

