2.9 Sample size justification

We expect a 90-day mortality of 40% in the standard arm. This mortality rate is compatible with 90-day mortality reported in contemporary cohorts of patients with RRT-requiring AKI in Finland and Australia/New Zealand.^{4,21} There is no clear guidance on the estimated risk reduction afforded by accelerated RRT so we have selected a relative risk reduction of 15% (absolute risk reduction 6%) as recommended by experts to be an effect magnitude that is minimally important and conceivable with this intervention.⁴⁹ With Type I error of 0.05 and power of 0.90, a sample size of 1,359 patients/arm would be required (total 2,718). In order to account for the interim analyses, the required sample size increases to 2,780. After accounting for a combined rate of crossover and dropouts of 3% (as derived from the pilot phase), we will target a total sample size of 2,866.

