**STandard versus Accelerated initiation of Renal Replacement Therapy in Acute Kidney Injury
(STARRT-AKI): A Multi-Centre, Randomized, Controlled Trial**

**Statistical Analysis Plan
May 23, 2019
CONFIDENTIAL**

Principal Investigators:

[name] MSc FRCPC
Division of Critical Care Medicine, Faculty of Medicine and Dentistry
University of Alberta
Associate Professor, Division of Critical Care Medicine
University of Alberta
[name]
[name]
Edmonton, Alberta
[name]
[contact]
[contact]
Email: [contact]

[name], MDCM MPH FRCPC
Division of Nephrology, Department of Medicine
St. Michael's Hospital
Assistant Professor, Department of Medicine
University of Toronto
[name]
Toronto, Ontario
[name]
[contact]
[contact]
Email: [contact]

ClinicalTrials.gov Identifier: NCT02568722

Statistical analysis plan for the Standard versus Accelerated Initiation of Renal Replacement Therapy in Acute Kidney Injury (STARRT-AKI) trial

The optimal time for renal replacement therapy (RRT) initiation in critically ill patients with acute kidney injury (AKI) is uncertain and presents a dilemma for clinicians. ¹ Numerous observational studies that have described an association between the timing of RRT initiation and outcomes have been susceptible to bias and unmeasured confounding, ²⁻⁴ while recent randomised controlled trials ⁵⁻⁷ have disparate findings.

The Standard versus Accelerated Initiation of Renal Replacement Therapy in Acute Kidney Injury (STARRT-AKI) trial will be the largest trial to date to evaluate the timing of RRT initiation among critically ill patients with AKI. In this article we describe the pre-specified statistical analysis plan (SAP) for the STARRT-AKI trial finalised before the completion of targeted recruitment and locking of the trial database for analysis, in accordance with consensus recommendations.⁸

Trial design

The STARRT-AKI is a multinational, randomised, open-label, controlled trial of critically ill patients with severe AKI that is designed to compare the clinical and cost-effectiveness of a pre-emptive (accelerated) strategy of RRT initiation versus a strategy of watchful waiting and RRT initiation guided by AKI-related indications and clinician judgment (standard). ⁹ The protocol was finalised on 5 October 2015, without intervening amendments. ¹⁰

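### Protocol 2.8 names only a 90-day difference in RRT dependence as a reason to extrapolate costs and benefits beyond the trial; a survival difference, the primary hypothesis, is not named

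*Protocol*

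**What the plan says.** The SAP, under Trial design, describes the trial as "designed to compare the clinical and cost-effectiveness of a pre-emptive (accelerated) strategy" against watchful waiting, so the economic comparison is a stated purpose. Protocol 2.8 says that survival, RRT dependence, utility and costs will all be available for it. The same section then turns to the time horizon: "If RRT dependence at 90 days differs between the two treatment arms, then extrapolation of the benefits and costs beyond the timeframe" of the trial will be required. The next step is tied to that sentence: "To enable this, a decision analytical framework will be developed alongside the data from the clinical trial", with a lifetime perspective and sensitivity analysis for long-term uncertainty.

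The horizon without extrapolation is one year. Protocol 2.5.2 lists "Health care costs through day 365", and 2.7.2 counts "the costs associated with RRT use after ICU discharge up to 365 days from randomization". Section 2.4 makes follow-up to one year conditional on feasibility.

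The outcome named in the condition is the principal secondary outcome, "RRT dependence at 90 days among surviving patients" (2.5.2; also 1.2 and 2.10). The primary outcome is different: "The primary outcome will be all-cause mortality within 90 days of randomization" (2.5.1). The SAP, under Analysis principles, leaves one-year and health-economic outcomes to separate reporting, so it does not add to or change what 2.8 says.

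**The concern.** A treatment that saves lives produces most of its health gain after the first year. It also produces later costs, including dialysis for those of the extra survivors who remain dependent. Both lie outside a 365-day horizon. Section 2.8 recognises that long-term outcomes and costs matter to payers, yet the only circumstance it names for looking at them is a difference in RRT dependence. The result that the trial is powered for, fewer deaths, is absent from the condition.

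Two features make RRT dependence a poor sole trigger. It is compared among survivors, and both Protocol 2.10 and the SAP (Analysis of other secondary outcomes) warn that leaving out the dead may undo the balance given by randomisation. In addition, no criterion is given for when the arms differ, and the SAP avoids formal hypothesis testing of secondary endpoints. The horizon of the economic evaluation could therefore be settled after the results are known.

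**Working it through.** **1. The survival effect in the plan (Protocol 2.9).** Inputs: 90-day mortality 40% and 34%, two-sided type I error 0.05, power 0.90. With pooled variance and no continuity correction,

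n per arm = [1.960 × √(2 × 0.37 × 0.63) + 1.282 × √(0.40 × 0.60 + 0.34 × 0.66)]² / 0.06² = 1,359, or 2,718 in total, as stated.

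The increase to 2,780 for interim analyses is taken as stated. Then 2,780 / 0.97 = 2,866, as stated, or 1,433 per arm. None of these figures is in dispute; they fix the survival effect used below.

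**2. The design scenario set against the condition.**

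- Survivors, standard arm: 1,433 × 0.60 ≈ 860.
- Survivors, accelerated arm: 1,433 × 0.66 ≈ 946.
- Difference: 1,433 × 0.06 ≈ 86. At the 3,000 patients to which the SAP extends recruitment, it is 1,500 × 0.06 = 90.

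Suppose the same share of survivors is RRT-dependent in both arms. The comparison among survivors then shows no difference, and the stated condition is not met despite 86 more survivors. Equal shares do not mean equal costs either: at an assumed 10% dependence, 86 × 0.10 ≈ 9 more patients in the accelerated arm are on dialysis.

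**3. How much of the survival benefit falls within one year.** The documents give no life expectancy or utility, so this is an illustration. Let L be the mean remaining life in years of each extra survivor, counted from randomisation, and u a constant utility. Without discounting, per randomised patient:

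- one-year gain: at most 0.06 × 1 × u
- lifetime gain: 0.06 × L × u
- share captured in one year: at most 1/L, whatever the value of u

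| Assumed L (years) | Life-years gained per patient, lifetime | Share within one year (at most) |
|---|---|---|
| 3 | 0.18 | 33% |
| 5 | 0.30 | 20% |
| 10 | 0.60 | 10% |
| 15 | 0.90 | 7% |

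**4. Sensitivity to discounting.** At an assumed 5% a year, L years are worth (1 − 1.05^−L) / (1 − 1.05^−1) first-year equivalents: 4.5 for L = 5 and 10.9 for L = 15. The shares become 1/4.5 ≈ 22% and 1/10.9 ≈ 9%. One year still captures the smaller part.

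**The case against.** The strongest reply is that the sentence says *if*, not *only if*. It gives one circumstance in which extrapolation is needed and is silent about others. A reader might infer that 2.8 bars lifetime modelling after a survival-only result; the text does not say that. The section also opens by calling long-term outcomes and costs important, lists survival first among the inputs, and has the framework developed alongside the trial, which can be read as a plan to build the model in any case. All of this stands. What remains is that the model's introduction refers back to the condition, and that no passage in either document names survival as a reason to extrapolate.

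A second reply concerns the denominator. Section 2.8 does not itself restrict RRT dependence to survivors. Counted per randomised patient, equal shares among survivors would give slightly different proportions (at an assumed 10%, 6.0% against 6.6%), and the condition could be called met. This is possible, but 1.2, 2.5.2 and 2.10 all state this outcome among survivors. That the condition can be read both ways is itself a reason to replace it.

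Third, the detailed economic methods lie outside these documents and may settle the matter. That cannot be checked here, and it would not make the wording of 2.8 complete.

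**Conclusion.** The point holds as an incomplete stated trigger. If 2.8 is followed as written, a trial that succeeds on survival with equal RRT dependence among survivors could have its economic value measured to day 365 only. That would omit roughly two thirds or more of the survival benefit when the extra survivors live 3 years on average, and about 93% or more when they live 15. These shares rest on an assumed remaining life, constant utility and no discounting; discounting softens them without changing the direction.

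A reader might invert the shares and infer that cost per QALY would be overstated by the same factor. The documents do not support that step. It holds costs at one year, whereas the extra survivors would also incur lifetime costs, including dialysis, and these push the ratio the other way. The net effect on cost per QALY is not quantified.

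Severity is minor. Only the economic evaluation is affected, and the SAP reports that after the main findings. Survival, RRT status, utility and costs are planned for collection whatever the trigger says. The primary mortality analysis and sample size are unaffected.

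**What to change.** Replace the condition in Protocol 2.8 with a statement along these lines: *The lifetime decision model will be run whatever the 90-day results. It will be driven jointly by the three Day-90 states (dead, alive on RRT, alive and RRT-free), with their uncertainty carried through to costs and QALYs. The within-trial result to day 365 will be reported beside it.*

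The three states are already defined in Protocol 2.10 and in the SAP under Analysis of other secondary outcomes, and the decision model is already described in 2.8. Any separate economic analysis plan should carry the same sentence.

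The cost is small: one sentence and no new trial data. The downside is that modelling is done even when the arms look similar, and its results depend on long-term assumptions, which must be stated and varied in the sensitivity analysis already promised.
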